1.0 Study Summary

Study Title	Use of ICG-fluorescence imaging for sentinel lymph node mapping in patients with breast cancer
Brief Summary	The primary objective is to determine the feasibility of using ICG fluorescence through the Asimov Imaging Platform for sentinel lymph node mapping by comparing lymphatic visualization using blue dye and technetium sulfur colloid (standard of care) versus ICG fluorescence imaging. We will enroll 10 patients and assess the image acquisition parameters of using ICG fluorescence through the Asimov Imaging Platform for sentinel lymph node mapping
Number of study sites	One
Study Design	Prospective, single arm feasibility study
Primary Objective	To determine the feasibility of using ICG fluorescence through the Asimov Imaging Platform for sentinel lymph node mapping by comparing lymphatic visualization using blue dye and technetium sulfur colloid (standard of care) versus ICG fluorescence imaging.
Secondary Objective(s)	To assess the image acquisition parameters of using ICG fluorescence through the Asimov Imaging Platform for sentinel lymph node mapping
Research Intervention(s)/ Investigational Agent(s)	ICG-fluorescence Imaging
Drugs/devices used on study (including any IND/IDE #)	Onlume Asimov Imaging Platform
Study Population	Breast cancer patients with clinical T1 or T2, node negative breast cancer undergoing sentinel lymph node mapping
Sample Size	10
Study Duration for individual participants	21 days (day of procedure and post-operative visit)
Study Specific	NA
Abbreviations/ Definitions	

Note: Include only elements relevant to this study.

2.0 Background

2.1 Sentinel lymph node (SLN) mapping is the current standard of care to stage the axillary lymph nodes for women with clinically node negative axilla.¹⁻³ Mapping is most commonly performed with radioisotope technetium-99 sulfur colloid and/or vital blue dye. Using this approach, mapping rates exceed 95% with a low false negative rates (5-10%).³⁻⁵

Although the current approach is effective, there are some gaps. Technetium-99 sulfur colloid is often injected in nuclear medicine prior to the operating room (either same day or day prior). This adds complexity to scheduling of operating room cases as well as cost. In addition, technetium-99 sulfur colloid is an ionizing agent which means that this approach cannot be used in hospital settings without a nuclear medicine department. It also requires extensive safety protocols to be in place. Finally, national shortages in technetium-99 sulfur colloid have been experienced during and since the pandemic which highlight the need for an alternative mapping agent.

In addition, there are some limitations to the use of technetium-99 sulfur colloid for SLN mapping from a patient perspective. The same scheduling issues regarding injection can be inconvenient for patients, especially those that live further from the hospital. Similarly, these injections can be very painful, given they occur at the edge of the areola.^{7,8} Patients often ask why these injections can't happen intra-operatively after they have received anesthesia; this is not feasible for many nuclear medicine departments workflow.

2.2 Indocyanine green (ICG) has been described as a dye for SLN mapping since the early 2000's.⁹ A recent clinical trial comparing SLN identification rates for 100 patients receiving technetium colloid, blue dye, and ICG demonstrated non-inferiority between ICG and technetium colloid, with successful mapping of 96.1%.¹⁰

ICG is increasingly used in breast cancer surgery for a variety of indications, including lymphatic mapping for lymphedema treatment and assessment of tissue viability during reconstruction. 11-18 Consequently, many centers have already overcome one of the most significant barriers to the use of ICG mapping, specifically that it requires an intra-operative imaging device. Given the potential to cut costs and improve patient experiences by avoiding the pre-operative injection, there is value in considering the use of ICG for SLN mapping.

Several potential challenges to using ICG for SLN mapping exist. First, challenges exist related to the devices used to detect ICG fluorescence. Many devices designed for ICG cannot optimally be used with ambient light, making it challenging to use to actively guide surgical dissection into the OR. In this proposal, we will determine the feasibility of using the Asimov Imaging Platform for fluorescence-guided surgery in the operating room. The Asimov can be used without altering external (i.e., room) light functionality or levels. In addition, it is mounted on an arm that can be positioned over the operative field. This facilitates real-time

visualization of lymphatics to support sentinel lymph node mapping during the dissection and would represent a significant advancement.

The second challenge relates to the penetration of the ICG imaging through skin and soft tissue. With the technetium, the option exists to obtain an image in radiology confirming the mapping was successful before coming to the OR; this allows for the potential for a second injection if needed for slow mapping. In the OR, a handheld probe is then used to localize the location of the lymph nodes in order to plan placement of the axillary incision. However, ICG fluorescence does not have the same depth of tissue penetration as technetium. In a recent clinical trial, the lymph nodes were not able to be visualized prior to skin incision using a hand-held fluorescence imaging device called Fluobeam 800. Consequently, the investigators planned their skin incision to be just lateral to the pectoralis muscle (where the majority of breast lymph nodes are located). Importantly. the ICG fluorescence was successful in identifying the sentinel lymph nodes once the skin incision was made. Given variation in device design, it is important to assess the feasibility of the Asimov Imaging Platform in identifying sentinel lymph nodes prior to and after skin incision.

The objective of this study is to assess the feasibility of using fluorescence-guided surgery with ICG dye through the Asimov Imaging Platform for the sentinel lymph node mapping. We will continue to use blue dye and technetium sulfur colloid to guide clinical decision making (standard of care).⁶ We will then compare the ICG fluorescence findings using the Asimov imaging Platform (research) with the blue dye and technetium sulfur colloid (standard of care).

3.0 Study Objectives and Endpoints

Specific Aim 1: To determine the feasibility of using ICG fluorescence through the Asimov Imaging Platform for sentinel lymph node mapping by comparing lymphatic visualization using blue dye and technetium sulfur colloid (standard of care) versus ICG fluorescence imaging.

Specific Aim 2: To define optimal image acquisition parameters of using ICG fluorescence through the Asimov Imaging Platform for sentinel lymph node mapping to inform the clinical workflow.

- 2a. To define dynamic range of ICG fluorescence signal in lymph nodes and background tissue.
- 2b. To assess image contrast as a function of ICG dose and time post-injection.

4.0 Number of Participants

We plan to enroll 10 patients in this feasibility pilot study.

5.0 Inclusion and Exclusion Criteria

5.1. Screening and recruitment: Patients being cared for by [name] within the UW Breast Center will be eligible for consideration. [name] will identify eligible patients from her clinical practice.

5.2 Inclusion criteria:

- ≥ 18 years of age
- Diagnosis of clinical T1 or T2 breast cancer clinically node negative breast cancer requiring surgical lymph node evaluation
 - Surgery at University of Wisconsin Hospital and Clinic

5.3 Exclusion criteria:

- Pregnant: It is not known whether indocyanine green can cause fetal harm when administered to a pregnant woman or can affect reproduction capacity. Women of child-bearing age will undergo a urine pregnancy test on the day of surgery, which is standard of care prior to anesthesia.
- Breastfeeding: It is not known whether this drug is excreted in human milk.
 Because many drugs are excreted in human milk, caution should be exercised when indocyanine green is administered to a nursing woman.
 We will exclude women who are breastfeeding.
- Unable to provide informed consent
- Allergy to indocyanine green
- History of ipsilateral breast or axillary surgery

6.0 Special Populations

We will not enroll special populations in this feasibility pilot study.

7.0 Recruitment Methods

- 7.1 [name] will identify eligible patients from her clinical practice.
- 7.2 [name] will introduce the study to them at the time of their clinic visit. A member of the study team will then discuss the study in detail with interested patients. As much time as needed will be given for potential subjects to decide whether or not to participate in this study. Subjects will be informed that they are not obligated to participate in the study.

8.0 Consent/Assent Process

The consent process will occur either at the Breast Center or in the pre-operative area on the day of surgery, based on whether a member of the study team is available to approach the patient on the day of their clinic visit. Patients will then be consented in a closed private room. Subjects will receive a copy of the consent form and will be given contact information for member of the study team and PI for any additional questions.

9.0 Setting

Patients will be recruited from the UW Breast Center. Surgery will occur within the operating rooms at UW Health.

10.0 Study Intervention

Standard of Care Procedures:

SLN mapping using technetium-99m +/- isosulfan blue dye: For patients enrolled in the study, sentinel lymph node mapping and biopsy will be performed using technetium-99m sulfur colloid and isosulfan blue dye (unless there is a contraindication to blue dye); this is an acceptable standard of care. Injection of the technetium-99m sulfur colloid will be performed by the nuclear medicine team as per standard of care. The isosulfan blue dye injection will be performed by the participating surgeon in the operating room; as per standard of care, injection will be subareolar. Incisions will be planned based on the technetium-99m activity or at the lateral aspect of the pectoralis muscle, per usual care.

Research Procedures:

SLN mapping with ICG fluorescence using the Asimov Platform: The research procedures will include using ICG-fluorescent imaging for the SLN mapping. OnLume will provide a sterile drape designed specifically for the OnLume Asimov Platform. 25 mg of ICG and 10 mg Sterile Water will be dispensed for injection by UW Health pharmacy. Before the image acquisition of each patient, ICG will be reconstituted under sterile conditions with Sterile Water (2.5 mg/1 ml). The vial will be gently shaken to dissolve. Reconstituted ICG must be used within 6 hours after reconstitution. The total dose of dye will be kept below 2 mg/kg of patient body weight. The dose of ICG to be injected is based on the existing literature. 9,10 2 ml (5 mg) of ICG solution will be injected intradermally in 1-4 injection sites in the lateral areolar region. After injection, gentle manual massage will be performed for 5 minutes. ICG imaging will be obtained prior to incision. After incision is made (following standard of care procedures), the axilla will be visualized using the Asimov Platform to assess for ICG-fluorescence in sentinel lymph nodes.

Impact on clinical care of the ICG mapping: The objective of this study is to evaluate the feasibility of using ICG fluorescent imaging through the Asimov Imaging Platform for SLN mapping. Compared to other platforms, the Asimov Imaging Platform allows real time imaging without altering ambient light. Clinical decisions regarding which lymph nodes are considered sentinel lymph nodes (and should be removed) will be made based technetium-99 activity and/or vital blue dye, as per standard of care. However, we will image with the Asimov Platform throughout to determine whether ICG-fluorescent imaging would have led to identification of different lymph nodes.

11.0 Study Timelines

The duration of an individual participant's participation is limited to the OR day and the post-operative visit. We anticipate enrolling the 10 participants in <12 months.

12.0 Procedures Involved

Patients will be consented either in clinic or on the day of surgery. A medical record review will collect pre-operative and post-operative data. We will inject the ICG and

collect imaging data as described above. We will collect procedural data related to the ICG injection and fluorescent imaging. We will assess adverse events related to the injection at the post-operative visit.

Overview of Study Calendar

Visit Number	Screening/recruitment	Pre-op	Day of	Post-op	Post-op
		Medical	Surgery	Visit .	Medical
		Record			Record
		Review			Review
Informed Consent/Assent	X				
Review Eligibility	X				
Demographics/prior		Χ			
medical history/clinical					
tumor characteristics					
Pregnancy Test			Χ		
Operative data collection			Χ		
Fluorescent Imaging Data			Χ		
Pathologic tumor					Х
characteristics					
Adverse Event			Χ	Х	
Assessment					

Medical Record Review: We will collect data through UW Health electronic medical record review. We will record limited demographics about the patient including: age, race/ethnicity, BMI, type of breast surgery, receipt of neoadjuvant systemic therapy, prior receipt of radiation, clinical and pathologic cancer stage (tumor size and lymph node status), and receptor status (estrogen receptor, progesterone receptor, her2neu). We will also collect surgical and pathologic details related to breast/axillary surgery.

Operative data collection:

We will collect the following procedural data:

- We will document whether ICG-fluorescence is visualized prior to incision (yes/no).
- At each time point when the axilla is examined for technetium-99
 activity, we will document whether technetium-99 activity, ICGfluorescence and blue dye is visualized We will also document
 whether lymphatic vasculature is visualized with the ICGfluorescence or blue dye.
- Each lymph node removed will be assessed for blue dye, technetium-99 activity, and ICG fluorescence and the findings recorded.
- Time ICG is mixed, injection, time of start and end of massage, start of axillary surgery, time of removal of lymph nodes, time of fluorescent imaging

- Number of lymph nodes removed. For removed lymph nodes, we will record whether removed lymph nodes had radiotracer, blue dye, or fluorescence.
- After removal of sentinel lymph nodes, we will document whether there is residual background technetium-99 activity and ICGfluorescence in the axilla.

Imaging data:

Subjects will receive fluorescence imaging using the Asimov Imaging Platform. Beginning at the time of ICG injection, image and video capture of contemporaneous white light reflectance and fluorescence imaging will be collected. Following the operation, post-processing will be conducted to elucidate injection technique superiority. We will use quantitative fluorescence to define optimal image acquisition parameters. In order to evaluate injection technique performance, the critical image acquisition parameters that provide surgeons detectable contrast (CNR) and fluorescence intensities in the lymphatic vessels and SLN will be measured with respect to post-injection time at each time point the axilla is examined.

Adverse Event Assessment: We will assess for complications related to the injection of the ICG intraoperative and at the post-operative visit.

Regulatory status of drugs and devices:

The Onlume Asimov Imaging Platform is a non-significant risk device. A letter supporting this is attached.

ICG is FDA approved as an optimal imaging agent for visualization of lymph nodes and lymphatic vessels. The Investigational Drug Brochure is attached to this application. ICG contrast meets requirements for IND exemption because:

- (i) ICG is lawfully marketed in the United States
- (ii) The investigation focuses on the Asimov Imaging Platform is not intended to be reported to FDA in support of a new indication for use nor intended to support any other significant change in the labeling for ICG;
- (iii) This investigation focusing on the Asimov Imaging Platform is not intended to support a significant change in the advertising for ICG;
- (iv) The investigation does not involve a route of administration or dosage level or use in a patient population or other factor that significantly increases the risks (or decreases the acceptability of the risks) associated with the use ICG. ICG has been used extensively in clinical practice with an exceedingly good safety profile.
- (v) The investigation is conducted in compliance with the marketing limitations described in 21 CFR § 312.7.

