19.0 Study Analysis

Baseline demographic and outcome variables will be summarized using descriptive statistics. We will report whether ICG-fluorescent lymph nodes were visualized percutaneously (prior to incision). We will describe concordance rates between technetium-99 and ICG-fluorescence for each sentinel lymph node removed (mean 2.8 nodes with a standard deviation of 2.2). We will also assess concordance at the patient level; using the technetium-99 as the gold standard,

we will describe the number of lymph nodes that would have been missed (i.e. technetium-99 + but ICG- in removed SLN) or would have been excised unnecessarily (i.e. residual ICG-fluorescence in axilla but no residual technetium-99) if ICG-fluorescent imaging had guided the SLN. We will summarize any adverse events.

Planned reporting of concordance rates between technetium-99 and ICG per excised sentinel lymph node						
Technetium-99 + Technetium-99 - Total						
ICG +						
ICG -						
Total						

20.2 Sample Size Justification:

No power calculation is calculated for this feasibility study. We anticipate that the sample size of 10 will be enough to assess initial feasibility of this approach and whether further study is warranted.

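### The rule for lymph nodes that ICG would have removed unnecessarily rests on a field recording only whether residual signal is present in the axilla, so non-nodal fluorescence can be scored as a node

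*Combined protocol and SAP*

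**What the plan says.** Section 19 takes technetium as the reference ("using the technetium-99 as the gold standard") and promises results in nodes: "we will describe the number of lymph nodes that would have been missed", or that "would have been excised unnecessarily (i.e. residual ICG-fluorescence in axilla but no residual technetium-99". The bracket acts as the definition of an unnecessary excision.

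The data item that feeds this definition is in Section 12, under operative data collection. Once the sentinel nodes have been removed, the team documents whether there is "residual background technetium-99 activity and ICGfluorescence in the axilla". The item asks about presence in the axilla. It does not ask for the source of the signal or the number of sources.

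Node-level findings are planned only for excised tissue: "Each lymph node removed will be assessed for blue dye, technetium-99 activity, and ICG fluorescence and the findings recorded". Section 10 says that the decision on which nodes to take "will be made based technetium-99 activity and/or vital blue dye, as per standard of care". ICG does not guide removal.

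Elsewhere the plan keeps node, vessel and background apart. Aim 2a in Section 3 is "To define dynamic range of ICG fluorescence signal in lymph nodes and background tissue". Section 12 records whether lymphatic vessels are seen with ICG or blue dye when the axilla is examined for technetium, and its imaging paragraph plans intensity measurements in vessels and in sentinel nodes.

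**The concern.** The quantity to be reported is a number of lymph nodes, but the quantity recorded is whether the axilla still fluoresces. The two agree only if all residual fluorescence is nodal. The plan does not say that it is, and it measures vessel and background signal as separate things elsewhere.

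The gap cannot be closed from specimens. A residual ICG-only signal stays in the patient unless technetium or blue dye gives a separate reason to remove the tissue, so the analyst will not have a node in hand to confirm or refute it. The source has to be judged at imaging or from the video, and the plan requires neither.

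At stake is the over-excision side of the patient-level comparison with technetium, in a pilot meant to show whether further study is worthwhile. A vessel or diffuse glow entered as a node would count against ICG without evidence that any node would have been taken.

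This is separate from the fact that a yes/no field cannot give a count. Counting foci without classifying them would leave the problem in place, because some of the counted foci could be vessels.

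**Working it through.** There is no figure in the plan to reproduce. The sample size of 10 is given without a calculation, and Section 19 is descriptive with no intervals planned. The check is therefore a comparison of the rule with the data, followed by an illustration of scale.

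**Step 1: apply the rule to each possible finding.**

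| Finding | Scored as unnecessary excision? | Is that right? |
|---|---|---|
| Residual ICG from a discrete node, no residual technetium | Yes | Yes |
| Residual ICG from a vessel or diffuse tissue, no residual technetium | Yes | No, spurious |
| Residual ICG-only node, residual technetium elsewhere in the same axilla | No | No, a true one is lost |
| Residual ICG from a vessel or diffuse tissue, residual technetium present | No | Yes |
| Removed node, ICG positive and technetium negative (for example taken for blue dye) | No; it appears only in the 2x2 table | Outside the rule |

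Row 2 is the point made here, and by itself it can only raise the count. Rows 3 and 5 leave ICG-positive, technetium-negative nodes out of the count. The net direction therefore cannot be derived from the documents.

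**Step 2: scale, for illustration only.**

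Inputs from the documents: 10 patients (Section 4); mean 2.8 nodes removed per patient (Section 19), so 10 × 2.8 = 28 removed nodes expected.

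Assumed input: q, the share of patients with non-nodal residual ICG and no residual technetium. The documents give no value, so a range is shown. Each flagged axilla is taken as one node, which is a second assumption, since a presence/absence field yields no node count.

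- Expected spurious flags = 10 × q
- Relative to removed nodes = 10q / 28
- Chance of at least one = 1 − (1 − q)^10

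| q (assumed) | Expected spurious flags | As % of 28 | Chance of at least one |
|---|---|---|---|
| 0.1 | 1 | 3.6% | 1 − 0.9^10 = 65% |
| 0.2 | 2 | 7.1% | 1 − 0.8^10 = 89% |
| 0.3 | 3 | 10.7% | 1 − 0.7^10 = 97% |
| 0.5 | 5 | 17.9% | 1 − 0.5^10 = 99.9% |

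Expressed by patient, each such axilla moves the flagged share by 1/10, or 10 percentage points. This shows how sensitive a study of 10 is to a single misclassified axilla. It does not estimate how often that will happen.

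**The case against.** The strongest reply is that Section 19 speaks of lymph nodes throughout and the bracket only glosses that count. Section 10 states the purpose at node level: imaging continues throughout to see whether ICG would have pointed to different nodes. A sensible investigator would not enter diffuse glow as a node. In addition, vessel visualization may already be recorded at the post-removal check if that counts as an examination for technetium, and video runs from the time of injection. On this view the plan is merely terse.

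Part of this stands. The intent is nodal and much of the raw material will exist. But the definition as written has no step that excludes non-nodal signal. A note that vessels were seen does not say whether the residual signal was a vessel, and Section 19 does not use the vessel record or the video for this count. The investigator's good sense would be an unrecorded judgement.

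Three stronger readings are tempting, and the documents do not support them:

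- A reader might infer that the field measures background ICG by design. In the Section 12 wording, the word background may qualify technetium only, and Section 19 omits it. The point does not depend on that word.
- A reader might infer that Aim 2a predicts visible glow after node removal. It plans to measure signal in background tissue and does not say what will be seen in the bed afterwards.
- A reader might infer that this count is one of only two places where ICG errors appear. The 2x2 table also shows both kinds of discordance among excised nodes.

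**Conclusion.** The concern holds as a mismatch between an endpoint and its data. The rule counts nodes, the field records residual signal of unstated source, and no specimen or planned classification links the two. Non-nodal ICG signal in an axilla without residual technetium would meet the rule, and by this route it can only add spurious counts.

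The size is unknown because no frequency is given. For scale, one such patient is 1 of 10 flagged. The probabilities and percentages in the working rest on assumed values of q and on one node per flagged axilla.

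A reader might go on to conclude that the trial will overstate over-excision by ICG. That does not follow, because the same rule also leaves out true ICG-only nodes when technetium remains in the axilla, and ICG-positive, technetium-negative nodes that were removed. The net direction is undetermined.

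The study is a small descriptive pilot in which ICG does not steer surgery, so this threatens the interpretation of one reported measure and not patient care. It should still be corrected before data collection, because the source of the signal is best judged when it is seen.

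**What to change.** In Section 12, replace the single post-removal ICG item with one entry for each residual ICG focus, classed as discrete nodal focus, lymphatic vessel or diffuse background. Add a short prespecified definition of a discrete focus, worded so that a second reader can apply it to the captured video. The documents contain no visibility rule for removed nodes that could be borrowed, so the definition has to be written. Note the technetium finding beside each discrete focus at the time, because the video cannot supply it later.

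In Section 19, count as unnecessary excisions only discrete nodal foci without technetium activity. Report vessel and diffuse signal separately, by patient, where they also serve Aim 2a.

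The cost is one expanded case-report field, one definition and one sentence of analysis text, using imaging that is already planned. The downside is that deciding what counts as a discrete focus remains a judgement; keeping the video allows it to be re-read. Surgical decisions do not change.
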